4.6.4 Precautions

Combination therapy may result in unexpected toxicity especially in novel combinations with other immune modifying agents. A striking example in macaques is presented in Vaccari, *et al.* 2012.

Please note that while unproven, there is a suggestion that autoimmune events, including hepatitis, may occur more frequently at sites of metastases or prior injury.

Caution is advised when considering treatment with high dose IL-2 in participants who have previously been administered ipilimumab, particularly in participants who experienced ipilimumab-related diarrhea/colitis. Colonoscopy or sigmoidoscopy with biopsy may be advisable prior to IL-2 administration once the participant is no longer receiving ipilimumab.

Participants who have received ipilimumab may potentially develop autoimmune disease with subsequent therapy including the appearance of colitis, hypophysitis, or adrenal insufficiency.

4.7 **Duration of Therapy**

In the absence of treatment delays due to AE(s), treatment may continue 92 weeks of nivolumab (with ipilimumab, if receiving dose level 2 or -2) until one of the following criteria applies:

• The development of progression (confirmed PD by RECIST Criteria or PD by the KS evaluation criteria in Section 9.2 or per Section 9.3, utilizing the consensus RECIL (2017). Participants will remain on study treatment until progression is confirmed,

Pregnancy

- All WOCBP should be instructed to contact the investigator immediately if they suspect they might be pregnant (e.g., missed, or late menstrual period) at any time during study participation. Institutional policy and local regulations should determine the frequency of on study pregnancy tests for WOCBP enrolled in the study.
- o The investigator must immediately notify CTEP in the event of a confirmed pregnancy in a study participant.
- Intercurrent illness that prevents further administration of treatment.
- Unacceptable AE(s) which include the following (see also Section 6.0 and specific algorithms in Appendix X):
 - o Any grade 4 events except as noted below.
 - o Grade 3 drug-related autoimmune or inflammatory events including uveitis, pneumonitis, diarrhea, colitis, neurologic AEs, hypersensitivity reaction, or infusion reaction of any duration requires discontinuation except as noted below:
 - o Any other grade 3 non-skin, drug-related AE lasting >7 days including fatigue.

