 - o Any grade 3 or 4 drug-related laboratory abnormality or electrolyte abnormality,

- not associated with underlying organ pathology that does not require treatment except for electrolyte replacements **does not** require treatment discontinuation.
- o Grade 3 or 4 amylase or lipase abnormalities that are not associated with DM, associated liver or gall bladder inflammation clinical manifestations of pancreatitis and which decrease to ≤ Grade 2 within 1 week of onset **may** resume study treatment when resolved.
- Any grade 2 drug-related uveitis or eye pain or blurred vision that does not respond to topical therapy and does not improve to Grade 1 severity within the re-treatment period OR requires systemic treatment.
 - Participants requiring > two dose delays for the same type of event should go off protocol therapy.
 - Any AE, laboratory abnormality, or intercurrent illness, which, in the judgment of the investigator, presents a substantial clinical risk to the participant with continued study drug dosing.
- Any participants who require additional immune suppressive treatment beyond steroids should go off study treatment.
- In participants with HIV-cHL, any participant who requires consolidative therapy with high dose chemotherapy followed by stem cell transplantation will be permitted to go off study therapy.
- Withdrawal of informed consent (participant's decision to withdraw for any reason).
- General or specific changes in the participant's condition, or any clinical AE, laboratory abnormality or intercurrent illness, which, in the opinion of the investigator, indicate that continued treatment with study therapy is not in the best interest of the participant.
- Termination of the study by sponsor.
- Participants treated with systemic steroids, except for a short course of tapered steroids for grade 3 rash and physiologic replacement doses, should be off study.
 - Participants who have been treated with steroids and who do not have an immunologically based event (e.g., infectious pneumonia rather than lymphocytic pneumonitis) may be restarted on treatment if asymptomatic after 2 weeks off all steroids.
 - o Tumor assessments should continue as per protocol even if dosing is interrupted.

4.8 **Duration of Follow-Up**

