4.10 Criteria to Resume Treatment

Restarting applies only to grade 2 events and some grade 3 events (skin rash and thyroiditis). The protocol chairs emphasize stopping treatment and starting steroids earlier to obtain resolution with the possibility for restarting rather than waiting for higher grade events.

For non-autoimmune or non-inflammatory events, participants may resume treatment with study drug when the drug-related AE(s) resolve to Grade ≤ 1 or baseline value, with the following exceptions:

- Participants may resume treatment in the presence of Grade 2 fatigue
- Evaluation to exclude any additional immune-mediated events endocrine, GI, and liver/pancreas function as clinically indicated must be made prior to restarting.
- Non-drug-related toxicity including hepatic, pulmonary toxicity, diarrhea, or colitis, must have resolved to baseline before treatment is resumed.

If the criteria to resume treatment are met, the participant should restart treatment no sooner than the next scheduled time point per protocol. However, if the treatment is delayed past the next scheduled time point per protocol the treatment should resume at the earliest convenient point that is within the six-week delay period.

If treatment is delayed for > 35 days for participants on dose levels 1 or -1, or > 42 days for participants on dose levels 2 or -2 (> 56 days for participants on a steroid taper), the participant must be permanently discontinued from study therapy, except as specified in Section 4.7 (Duration of Therapy).

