^{*}Participants with any CNS events including aseptic meningitis, encephalitis, symptomatic hypophysitis, or myopathy, peripheral demyelinating neuropathy, cranial neuropathy (other than peripheral n. VII), GB syndrome, myasthenia gravis should be off study.

Recommended management: See Neurologic Adverse Event Management Algorithm ($\underline{\text{Appendix } X}$).

Endocrine Hypophysitis Adrenal Insufficiency	Management/Next Dose for Nivolumab and Combination
≤ Grade 1	Asymptomatic TSH elevation. Add hormone replacement as clinically indicated. Continue therapy.
Grade 2	Hold until participants are on a stable replacement hormone regimen. Resume at same dose level.
Grade 3	Hold until patients are on stable replacement hormone regimen. Resume at same dose level. If diagnosed with hypophysitis should hold therapy if occurring before cycle 5 but may begin nivolumab monotherapy when returned to grade 1 (no earlier than 6 week and by end of up to an 8-week delay).
Grade 4	Off protocol therapy

Note all participants with symptomatic pituitary enlargement, exclusive of hormone deficiency, but including severe headache or enlarged pituitary on MRI should be considered grade 3 events. Isolated thyroid or testosterone deficiency may be treated as grade 2 if there are no other associated deficiencies and adrenal function is monitored.

Please evaluate pituitary function before beginning steroid therapy or replacement therapy of any kind.

*Note participants with thyroiditis may be retreated on replacement therapy. Participants must be evaluated to rule out pituitary disease prior to initiating thyroid replacement.

Participants with symptomatic hyperthyroidism can be given a short course of a beta blocker (e.g., propranolol). Hyperthyroidism usually converts to hypothyroid within 4 weeks.

Recommended management: See Endocrine Management Algorithm (Appendix X).

Fever	Management/Next Dose for Nivolumab and Combination
≤ Grade 1	Antipyretic therapy if no evidence of infection.
Grade 2	Hold until ≤ Grade 1. Resume at same dose level.
Grade 3	Hold until ≤ Grade 1. Resume at same dose level.
Grade 4	Off treatment.

Participants with fever should be evaluated as clinically appropriate. Participants may experience isolated fever during infusion reactions or up to several days after infusion. Evaluation over the course of 1-2 weeks should be done for other autoimmune events that may present as fever.

See Section 4.12, infusion reactions.

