RESPIRATORY, THORACIO	C AND MEDIASTINAL DISORDE	RS	
	Pleural effusion ³		
	Pneumonitis ³		
		Respiratory, thoracic and mediastinal disorders - Other (bronchiolitis obliterans with organizing pneumonia (BOOP)) ³	

Adverse Events with Possible Relationship to Nivolumab (CTCAE 5.0 Term) [n= 2069]		Specific Protocol Exceptions to Expedited Reporting (SPEER)	
Likely (>20%)	Less Likely (<=20%)	Rare but Serious (<3%)	
SKIN AND SUBCUTANEOUS T	TISSUE DISORDERS		
		Erythema multiforme ³	
	Pruritus ³		Pruritus ³ (Gr 2)
	Rash maculo-papular ³		Rash maculo-papular³ (Gr 2)
		Skin and subcutaneous tissue disorders -Other (bullous pemphigoid)	
	Skin and subcutaneous tissue disorders - Other (Sweet's Syndrome) ³		
	Skin hypopigmentation ³		
		Stevens-Johnson syndrome	
		Toxic epidermal necrolysis	

¹This table will be updated as the toxicity profile of the agent is revised. Updates will be distributed to all Principal Investigators at the time of revision. The current version can be obtained by contacting [contact]. Your name, the name of the investigator, the protocol and the agent should be included in the e-mail.

³Nivolumab being a member of class of agents involved in the inhibition of "immune checkpoints", may result in severe and possibly fatal immune-mediated adverse events probably due to T-cell activation and proliferation. This may result in autoimmune disorders that can include (but are not limited to) autoimmune hemolytic anemia, acquired anti-factor VIII immune response, autoimmune aseptic meningitis, autoimmune hepatitis, autoimmune nephritis, autoimmune neuropathy, autoimmune thyroiditis, bullous pemphigoid, exacerbation of Churg-Strauss Syndrome, drug rash with eosinophilia systemic symptoms [DRESS] syndrome, facial nerve disorder (facial nerve paralysis), limbic encephalitis, hepatic failure, pure red cell aplasia, pancreatitis, ulcerative and hemorrhagic colitis, endocrine disorders (e.g., autoimmune thyroiditis, hyperthyroidism, hypothyroidism, autoimmune hypophysitis/hypopituitarism, thyrotoxicosis, and adrenal insufficiency), sarcoid granuloma, myasthenia gravis, polymyositis, and Guillain-Barre syndrome.

⁴Pancreatitis may result in increased serum amylase and/or more frequently lipase.

⁵Cytokine release syndrome may manifest as hemophagocytic lymphohistiocytosis with accompanying fever and pancytopenia.

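### Section 5.1 gives two opposite instructions for symptomatic grade 3 hypophysitis: off study in the Neurologic Events footnote, hold and restart in the Endocrine/Hypophysitis table

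*Combined protocol and SAP*

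**What the plan says.** All places are in the protocol.

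- **Section 5.1, Neurologic Events.** The footnote lists, among events that end participation, "symptomatic hypophysitis, or myopathy, peripheral demyelinating neuropathy, cranial neuropathy (other than peripheral n. VII), GB syndrome, myasthenia gravis should be off study". Its text states no grade. Its asterisk sits on the grade 1-or-below and grade 2 rows; the grade 3 and 4 rows already stop treatment.
- **Section 5.1, Endocrine/Hypophysitis/Adrenal Insufficiency, grade 3.** Hold until hormone replacement is stable, then resume at the same dose. The row adds: "If diagnosed with hypophysitis should hold therapy if occurring before cycle 5 but may begin nivolumab monotherapy when returned to grade 1", with a window of 6 to 8 weeks.
- **Note under that table.** It says that "all participants with symptomatic pituitary enlargement, exclusive of hormone deficiency, but including severe headache or enlarged pituitary on MRI should be considered grade 3".
- **Same table, grade 2.** "Hold until participants are on a stable replacement hormone regimen. Resume at same dose level". Hypophysitis appears only in the table heading.
- **Section 4.7.** "Grade 3 drug-related autoimmune or inflammatory events including uveitis, pneumonitis, diarrhea, colitis, neurologic AEs, hypersensitivity reaction, or infusion reaction of any duration requires discontinuation", subject to listed exceptions, none of which names hypophysitis. The nivolumab risk list in Section 6.1.1 counts it as autoimmune, under "endocrine disorders (e.g., autoimmune thyroiditis, hyperthyroidism, hypothyroidism, autoimmune hypophysitis/hypopituitarism, thyrotoxicosis, and adrenal insufficiency".
- **Section 4.10.** "Restarting applies only to grade 2 events and some grade 3 events (skin rash and thyroiditis").
- **Section 4.4.** A permanent stop within 6 weeks of the first dose is a DLT. So is a grade 3 or 4 event requiring permanent discontinuation of either drug.

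**The concern.** Hypophysitis is a recognised immune-related toxicity of both drugs, and the trial's primary objective is safety and feasibility. A site that meets a symptomatic grade 3 case finds two adjacent instructions in one section, one ending treatment and the other allowing it to restart. Following either would be protocol-compliant. At stake are consistent protection of participants after a serious immune event, a discontinuation summary (Section 10.1.2) that reflects toxicity rather than which line the site read, and, in the dose de-escalation strata, possibly whether an event counts as a DLT.

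**Working it through.** No figure in the plan needs reproducing. The check is a comparison of texts, followed by short date arithmetic for the DLT consequence.

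1. **Do the two instructions meet the same participant?** The footnote names symptomatic hypophysitis. The Endocrine table names hypophysitis in its heading and in its grade 3 row, and its note sends symptomatic pituitary enlargement to grade 3. A participant with severe headache and an enlarged pituitary on MRI falls under both.

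2. **Are the actions opposite?** Yes. The protocol uses off study and off protocol therapy interchangeably: pneumonitis uses the first at grade 2 and the second at grade 3, and Section 4.9, on removal from treatment, speaks of removal from study.

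3. **Does a written rule choose?** Section 5.1 ranks itself above Appendix X. That does not settle a conflict within 5.1, or between 5.1 and Sections 4.7 or 4.10.

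4. **Do Sections 4.7 and 4.10 choose?** Neither permits a grade 3 hypophysitis restart. But both are stricter than Section 5.1 for grade 3 immune events generally:

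| Grade 3 event | Section 5.1 | Sections 4.7 / 4.10 |
|---|---|---|
| Immune-mediated, general rule | Nivolumab monotherapy possible after resolution | Stop (4.7); not a listed restart (4.10) |
| Liver function, before cycle 5 | Nivolumab monotherapy possible | Not a listed restart (4.10) |
| Diarrhea/colitis | Nivolumab monotherapy possible | Named as requiring discontinuation (4.7) |
| Hypophysitis, before cycle 5 | Nivolumab monotherapy possible | Stop (4.7); not a listed restart (4.10) |

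5. **Other grades.** Grade 4 agrees: treatment stops. At grade 2 the Endocrine row allows continuing, Section 4.10 allows grade 2 restarts, and Section 4.7 exempts replacement-dose steroids. Only the footnote stops treatment, and only if it covers hormone-deficiency hypophysitis as well as CNS or mass-effect disease.

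6. **DLT status.** Inputs: 14-day cycles (Section 4.3), a 6-week DLT period (4.4), and delay limits in 5.1 of 35 days for single agent and 42 days for the combination (56 on high-dose steroids).
   - The DLT period ends at 6 × 7 = 42 days. Cycle 5 starts on day 4 × 14 + 1 = 57. Every in-period event therefore precedes cycle 5.
   - *Combination.* The row offers nivolumab alone, so ipilimumab is given up. Section 4.4 counts permanent discontinuation of either drug, so the event may be a DLT under either instruction.
   - *Single agent, with the window applied as length of delay.* The earliest restart is 6 × 7 = 42 days, beyond the 35-day limit. Treatment ends under the Endocrine row too, and the contrast largely disappears.
   - *Single agent, with the window read as study weeks (as the Liver row words its own), or with the before-cycle-5 sentence read as applying only to the combination.* Restart within 35 days is possible. The footnote then gives a permanent stop and a DLT; the Endocrine row gives hold and resume.

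**The case against.** The best defence is that the specific rule governs. The footnote concerns CNS events and is marked only on the two lowest neurologic rows, whereas the Endocrine table is headed for hypophysitis and is graded. Section 5.2 bases management on Section 5.1, Appendix X and the Investigator's Brochure, and Section 5.1 lets the physician vary the algorithms in particular circumstances. The Appendix X endocrine algorithm is a figure not available here. DLTs are also discussed centrally (Section 4.4).

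Much of this is fair, and specific-over-general is a natural reading, but it is not written down. Confining the footnote to lower grades would stop treatment for the milder event and restart it for the worse one. Confining it to CNS or mass-effect disease fails because the Endocrine note sends that picture to the grade 3 restart row. Whatever Appendix X shows, Section 5.1 overrides it where they differ. Central discussion limits inconsistent DLT classification, but it applies the protocol's own rules and does not decide whether a site restarts.

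A reader might also infer that the Endocrine row is the outlier, because the footnote and Sections 4.7 and 4.10 all point to stopping. The documents do not support that. Section 5.1 allows nivolumab monotherapy after other grade 3 immune events, so 4.7 and 4.10 reflect a general mismatch with 5.1 and say nothing particular to hypophysitis.

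**Conclusion.** The contradiction is explicit at grade 3 and unresolved by any written rule. Confidence in that core is high, and it should be fixed. At grade 2 it is arguable only. The size is one footnote phrase against one table row. The documents give no basis for an event rate, so no numerical effect is claimed.

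The consequences for participant safety and the discontinuation summary follow directly. The DLT consequence is conditional: it arises in some single-agent cases and depends on how the 6-to-8-week window and the 35-day limit are read.

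A reader might go further and infer that the Stratum 1 MTD is wrong. Nothing shows this. Section 2.3.8 reports three evaluable participants at dose level 1 without a DLT, Section 2.3.9 describes the combination dose as tolerable in Stratum 1, and no hypophysitis event is reported.

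**What to change.** 1. In the Neurologic Events footnote, replace the hypophysitis entry with a cross-reference making the Endocrine/Hypophysitis table the governing rule.
2. Have the clinical team choose. If restart is intended, add hypophysitis on stable replacement as a named grade 3 exception in Sections 4.7 and 4.10, and say whether it survives the Section 4.7 rule that participants treated with systemic steroids, "except for a short course of tapered steroids for grade 3 rash and physiologic replacement doses, should be off study". If stopping is intended, change the Endocrine grade 3 row to off protocol therapy for hypophysitis.
3. State whether the 6-to-8-week window means study weeks or length of delay, and make it consistent with the 35-day and 42/56-day limits.
4. State in Section 4.4 whether a switch to nivolumab monotherapy counts as a DLT.

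The cost is protocol wording only: no added participants, visits or procedures.

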5.2 Other Guidance

These original ipilimumab guidelines are for investigator information. Treatment management decisions should be based on the information in Section 5.1, treatment algorithms in Appendix X, and further information in the IB.

5.2.1 Treatment of infusion reactions associated with ipilimumab

Since ipilimumab contains only human protein sequences, it is less likely that any allergic reaction will be seen in participants. However, it is possible that infusion

of ipilimumab will induce a cytokine release syndrome that could be evidenced by fever, chills, rigors, rash, pruritus, hypotension, hypertension, bronchospasm, or other symptoms. No prophylactic pre-medication should be given unless indicated by previous experience in an individual participant. Reactions should be treated based upon the following recommendations.

- For mild symptoms (*e.g.*, localized cutaneous reactions such as mild pruritus, flushing, rash):
 - o Decrease the rate of infusion until recovery from symptoms, remain at bedside, and monitor participant.
 - o Complete the ipilimumab infusion at the initial planned rate.
 - Diphenhydramine 50 mg IV may be administered at the discretion of the treating physician and participants may receive additional doses with close monitoring.
 - Premedication with diphenhydramine may be given at the discretion of the investigator for subsequent doses of ipilimumab.
- For moderate symptoms (any symptom not listed above [mild symptoms] or below [severe symptoms] such as generalized pruritus, flushing, rash, dyspnea, hypotension with systolic BP >80 mmHg):
 - o Interrupt ipilimumab.
 - o Administer diphenhydramine 50 mg IV.
 - o Monitor participant closely until resolution of symptoms.
 - O Corticosteroids may abrogate any beneficial immunologic effect but may be administered at the discretion of the treating physician.
 - o Resume ipilimumab infusion after recovery of symptoms.
 - At the discretion of the treating physician, ipilimumab infusion may be resumed at one-half the initial infusion rate, then increased incrementally to the initial infusion rate.
 - o If symptoms develop after resumption of the infusion, the infusion should be discontinued and no additional ipilimumab should be administered that day.
 - o The next dose of ipilimumab will be administered at its next scheduled time and may be given with pre-medication (diphenhydramine and acetaminophen) and careful monitoring, following the same treatment guidelines outlined above.
 - At the discretion of the treating physician additional oral or IV antihistamine may be administered prior to dosing with ipilimumab.
- For severe symptoms (e.g., any reaction such as bronchospasm, generalized urticaria, systolic blood pressure <80 mm Hg, or angioedema):
 - Immediately discontinue infusion of ipilimumab and disconnect infusion

tubing from the participant.

- o Consider bronchodilators, epinephrine 1 mg IV or subcutaneously, and/or diphenhydramine 50 mg IV, with solumedrol 100 mg IV, as needed.
- o Participants should be monitored until the investigator is comfortable that the symptoms will not recur.
- No further ipilimumab will be administered.
- In case of late-occurring hypersensitivity symptoms (e.g., appearance within one week after treatment of a localized or generalized pruritus), symptomatic treatment may be given (e.g., oral antihistamine, or corticosteroids).

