4.11 Treatment of Nivolumab-Related and Ipilimumab Combination Infusion Reactions

Since ipilimumab and nivolumab contain only human immunoglobulin or immunoglobulin protein sequences, these agents are unlikely to be immunogenic and induce infusion or hypersensitivity reactions. However, if such a reaction were to occur, it might manifest with fever, chills, rigors, headache, rash, urticaria, angioedema, pruritus, arthralgia, hypoor hypertension, bronchospasm, or other symptoms.

All Grade 3 or 4 infusion reactions should be reported as a SAE if criteria are met. Infusion reactions should be graded according to NCI CTCAE version 5.0 guidelines.

Treatment recommendations are provided below and may be modified based on local treatment standards and guidelines as medically appropriate:

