4.11.3 For Grade 3 or Grade 4 symptoms

Severe reaction, Grade 3 symptoms: prolonged (*i.e.*, not rapidly responsive to symptomatic medication and/or brief interruption of infusion); recurrence of symptoms following initial improvement; hospitalization indicated for other clinical sequelae (*e.g.*, renal impairment, pulmonary infiltrates).

Grade 4 symptoms: life threatening; pressor or ventilatory support indicated.

Immediately discontinue infusion of nivolumab. Begin an IV infusion of normal saline, and treat the participant as follows. Recommend bronchodilators, epinephrine 0.2 to 1 mg of a 1:1,000 solution for subcutaneous administration or 0.1 to 0.25 mg of a 1:10,000 solution injected slowly for IV administration, and/or diphenhydramine 50 mg IV with methylprednisolone 100 mg IV (or equivalent), as needed. Participant should be monitored until the investigator is comfortable that the symptoms will not recur. Nivolumab will be permanently discontinued. Investigators should follow their institutional guidelines for the treatment of anaphylaxis. Remain at bedside and monitor participant until recovery from symptoms. In the case of late-occurring hypersensitivity symptoms (*e.g.*, appearance of a localized or generalized pruritus within 1 week after treatment), symptomatic treatment may be given (*e.g.*, oral antihistamine, or corticosteroids).

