5.0 DOSING DELAYS/DOSE MODIFICATIONS

5.1 Dose Modifications for Nivolumab and Nivolumab and Ipilimumab Combination

Participants with an overall response of SD, PR, CR, or unconfirmed PD (refer to Section 9.1 for RECIST Criteria, Section 9.2 for KS response evaluation, and Section 9.3 for the 2017 RECIL Criteria for response evaluation) at the scheduled response visits at week 8 and all subsequent visits day 1 of cycles 6 and 9 will be eligible to continue to receive study drug treatments provided that they also have an ECOG performance status score of ≤ 2 , and did not have a DLT or other safety risk requiring discontinuation of the study drugs, as defined below.

Please refer to Appendix X to the protocol for toxicity management algorithms, which include specific treatment guidelines. Where discrepancies occur between Section 5.1 and Appendix X, use the instructions in Section 5.1. These algorithms should be followed unless there are specific clinical circumstances for which the treating physician indicates variations or alternative treatment are needed.

Generally, we strongly encourage early evaluation, withholding drug, and appropriate treatment as indicated in the management tables and following event specific guidelines.

Table 2: Dose Modification Tables for Nivolumab and Nivolumab and Ipilimumab Combination

All Other Events*	Management/Next Dose for Nivolumab and Combination
≤ Grade 1	No change in dose.
Grade 2	Hold** until ≤ Grade 1 OR baseline. Resume at same dose level.
Grade 3	Hold** until ≤ Grade 1 continue at investigator discretion.
Grade 4	Off protocol therapy.

^{*} Not immunologically mediated (excluding clinically insignificant lab abnormalities, see Section 6.4.1)

Recommended management: As clinically indicated.

All Other Events**	Management/Next Dose for Nivolumab and Combination
≤ Grade 1	No change in dose.
Grade 2	Hold until \leq Grade 1 OR baseline. When resolved \leq Grade 1 and off steroids for at least 1 week, resume at same dose level.
Grade 3	Off protocol therapy (exceptions noted in 5.4). May resume nivolumab monotherapy if resolved to Grade 1 or less (off physiologic

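### Sections 4.11.3 and 5.2.1 print IV epinephrine doses that differ 4- to 10-fold for a severe infusion reaction, and the protocol leans towards 4.11 without saying so

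*Combined protocol and SAP*

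**What the plan says.** Two sections give emergency treatment for a severe infusion reaction.

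- **Section 4.11** is headed "Treatment of Nivolumab-Related and Ipilimumab Combination Infusion Reactions". For Grade 3 or 4 symptoms, 4.11.3 reads "Recommend bronchodilators, epinephrine 0.2 to 1 mg of a 1:1,000 solution for subcutaneous administration" or, by the other route, "0.1 to 0.25 mg of a 1:10,000 solution injected slowly for IV administration". These drugs are to be given as needed. The steps in 4.11.1 to 4.11.3 name only nivolumab.
- **Section 5.2.1**, on ipilimumab reactions, lists severe symptoms such as bronchospasm, angioedema and systolic pressure below 80 mm Hg. It then says "Consider bronchodilators, epinephrine 1 mg IV or subcutaneously, and/or diphenhydramine 50 mg IV, with solumedrol 100 mg IV, as needed". It prints no dilution and no rate.

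The status of each text is qualified. Section 4.11 says that its recommendations "may be modified based on local treatment standards and guidelines as medically appropriate", and 4.11.3 adds "Investigators should follow their institutional guidelines for the treatment of anaphylaxis". Section 5.2 opens with "These original ipilimumab guidelines are for investigator information" and refers treatment decisions to Section 5.1, Appendix X and the Investigator's Brochure (IB). Section 5.2.1 nevertheless tells the reader to treat reactions according to the list it gives.

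The only explicit precedence rule is in Section 5.1: "Where discrepancies occur between Section 5.1 and Appendix X, use the instructions in Section 5.1".

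**The concern.** Ipilimumab is never given alone in this trial. Under Section 4.3.2, when both drugs fall on the same day, nivolumab runs first, the line is flushed, and ipilimumab follows. A reaction on such a day can plausibly be read under the heading of 4.11 or under 5.2.1. A clinician looking for an intravenous epinephrine dose then finds either 0.1 to 0.25 mg, dilute and slow, or 1 mg with no dilution or rate, and no sentence that reconciles them.

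What is at stake is participant safety in a rare emergency. The text is consulted under time pressure, so an unreconciled dose of an emergency drug is worth removing even though local practice may override both sections. No estimate, test or decision rule depends on it.

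**Working it through.** **1. Dose figures, by route.** Inputs are from 4.11.3 and 5.2.1.

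| Route | 4.11.3 | 5.2.1 | Comparison |
|---|---|---|---|
| Intravenous | 0.1–0.25 mg, 1:10,000, slowly | 1 mg, no dilution or rate | 1 / 0.25 = 4; 1 / 0.1 = 10 |
| Subcutaneous | 0.2–1 mg, 1:1,000 | 1 mg | 1 mg is the top of the range; no conflict |

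The mismatch is therefore confined to the intravenous route. Neither section says whether its figure is per injection, and neither sets a cumulative ceiling.

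**2. Which text governs.** Following the protocol's own pointers:

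- Section 8.2.6 sends nivolumab reactions to 4.11 but ipilimumab reactions to 5.1.
- Section 5.1 has tables for many toxicities but none for infusion reactions. Its only pointer on the subject is the Fever note, which cites Section 4.12. Section 4 ends at 4.11, so 4.11 is evidently meant.
- Section 5.2 defers to 5.1, Appendix X and the IB, and does not name 4.11.
- The title of Appendix X does not list infusion reactions. Its figures and the IB were not available, and nothing is claimed about their content.
- The precedence rule in 5.1 covers 5.1 against Appendix X only.

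The informational label on 5.2 and the evident target of the Fever note both favour 4.11. Against that stand the directive wording inside 5.2.1 and the fact that 8.2.6 leads to a section with no infusion-reaction table. The preference for 4.11 has to be inferred.

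**3. Who could be concerned.** The maxima in Section 10.2 reproduce the plan's own total: 18 + 18 + 24 + 24 + 12 = 96. The single agent solid tumor cohort (24) and the cHL cohort (12) receive no ipilimumab: 96 − 24 − 12 = 60.

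That 60 still counts single-agent participants in the strata. Under Section 4.2, a single-agent maximum tolerated dose is settled in six participants before combination dosing opens, and Sections 4.2.2 and 4.3.3 start Stratum 2 on the single agent too. So at most 18 − 6 = 12 per stratum can start ipilimumab:

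- with a combination expansion of 24 (Section 10.2): 12 + 12 + 24 = 48;
- with a combination expansion of 12 (synopsis): 12 + 12 + 12 = 36.

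These are counts of evaluable participants; replacements could add a few. Within them, only participants who have a severe reaction and are given intravenous epinephrine are concerned. The documents give no rate for that. Section 4.11 calls such reactions unlikely. The risk lists in Section 6.1 place infusion related reaction in the column for events in up to 20% of patients for both agents, without severity, and a nivolumab footnote mentions high-grade hypersensitivity reactions.

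**The case against.** The strongest reply is that the protocol already ranks the two texts. Section 5.2 says that its content is for information and that decisions should rest elsewhere. Section 4.11 carries no such label, and its heading includes the combination. Read with the obvious correction, the Fever note in 5.1 also leads to 4.11. In addition, neither dose is mandated: both texts say as needed, 4.11 yields to local standards, and 4.11.3 yields to institutional anaphylaxis guidelines.

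Much of this stands. A reader might infer that the protocol leaves the choice wholly open; it does not, because the text leans towards 4.11. The deference to local practice also lowers the severity. But the lean depends on correcting a wrong section number and on reading a general preface as outranking directive wording placed beneath it. An emergency instruction should not need that.

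A reader might also infer that participants would receive 4 to 10 times too much epinephrine. The documents do not support that. The ratio compares printed figures, not drug given: both texts are advisory, and neither defines a total dose. They also describe severity differently, 4.11.3 by toxicity grade and 5.2.1 by a symptom list. Nor do the documents show which dose is medically correct.

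**Conclusion.** Wrong as written: an internal inconsistency in safety text, of low to moderate severity. The printed intravenous figures differ 4- to 10-fold, and only one of the two texts gives a dilution and a manner of injection. The subcutaneous figures agree. The protocol favours 4.11 by implication but nowhere says so.

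At most about 48 evaluable participants, or 36 with the smaller combination expansion, could start ipilimumab. This bound assumes that both strata complete six single-agent participants before combination dosing and that Stratum 2 follows the same sequence as Stratum 1. A reader might take 60 of 96 as the exposed group by subtracting only the two single-agent cohorts, but that overlooks the single-agent stage within each stratum. The number who would actually meet the conflicting text is smaller still and cannot be estimated from the documents.

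The mismatch itself is certain from the printed text. The statement about precedence is limited to the text that could be read. There is no effect on design, sample size or analysis.

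**What to change.** 1. Have the medical monitor confirm the intended intravenous dose.
2. Then either replace the epinephrine wording in 5.2.1 with the route-specific doses of 4.11.3 (0.2–1 mg of 1:1,000 subcutaneously, or 0.1–0.25 mg of 1:10,000 slowly by vein), or state that 4.11 supersedes 5.2.1.
3. Name ipilimumab alongside nivolumab in the steps of 4.11, so that they match its heading.
4. Correct the ipilimumab pointer in 8.2.6 (now 5.1) and the Fever note in 5.1 (now 4.12) so that both lead to 4.11.

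The cost is protocol wording and a notice to sites.
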